### 6.0 Procedures Involved\*

- 6.1 The study will be a randomized wait-list control design, with 50% of subjects receiving the intervention and 50% of subjects being on the wait-list.
- 6.2 Participants will be identified using the mass screening survey distributed to the pool of psychology students maintained by the

## PROTOCOL TITLE: An Exposure-Based Treatment for Perfectionism

psychology department (SONA) or using a brief, 3 question screener that includes three questions from the FMPS-CM. Participants who score a 8 or higher on the screener will be invited to participate in the current study and provided with the study passcode to sign up if they are interested. Additionally, an optional pre-screener not associated with research credit on SONA that includes the same three question screener that is used in the mass screener (3 items from the FMPS-CM) will be available for individuals who would like to participate in the study.

Once they sign up, all participants will be emailed a link to the informed consent form, which will be administered using a Qualtrics survey. All participants must first complete the informed consent before beginning other study procedures. After consenting, the participant will be directed to complete the FMPS. If the participant scores a 29 or lower on the FMPS-CM, they will be given credit for their time (.5 credits) and the experiment will end.

If they score a 29 or above on the FMPS, they will be emailed a link to a HIPAA-Compliant Zoom session scheduled for the appointment time for which they signed up on SONA. The HIPAA-Compliant Zoom meeting will have a waiting room and will be password protected. Participants will be directed to click on the HIPAA-Compliant Zoom link at the time in which their appointment starts. A member of the study team will administer the MINI International Neuropsychiatric Interview (MINI) and the Structured Clinical Interview for the DSM-IV (SCID) Cluster C Personality Disorders Modules via HIPAA-Compliant Zoom. Participants who do not meet inclusion criteria based on this clinical interview will be given .5 credits for their time and the experiment will end.

If participants meet inclusion criteria, they will be randomized to either the intervention group or the wait-list control group. 50% of subjects will be randomized to the treatment group and 50% of subjects will be randomized to the wait list group. Based on that randomization, they will be sent one to two Qualtrics links:

1. Wait List Qualtrics Link: This link will include questionnaires asking about their perfectionism, mood, and behaviors. A detailed list of questionnaires is provided below. After completing questionnaires, participants will be informed that they have been assigned to the wait list control group. They will be asked to complete the post-assessment questionnaires via a link that will be sent to them via email at the start of their post-assessment appointment time, which they signed up for on SONA. Additionally, they will be asked to refrain from seeking treatment for perfectionism for the duration of the study.

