## 2.0 Objectives\*

2.1 The purpose of this study is to test the efficacy of an exposure-based treatment for perfectionism. The aims of the study include:

- Evaluating whether a short-term computerized intervention can decrease perfectionism symptomatology (as measured by the Frost Multidimensional Perfectionism Scale (FMPS)).
- Seeing if this intervention also decreases levels of anxiety and depression, and possibly other symptoms related to obsessive-compulsive disorder (OCD) and eating disorders.

2.2 We hypothesize that the intervention group will have significantly lower levels of perfectionism symptoms than the wait-list control group at post-test. We also hypothesize that the intervention group will have decreased levels of anxiety and depression at post-test than those in the wait-list control group, after controlling for baseline scores.

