## PROTOCOL TITLE: An Exposure-Based Treatment for Perfectionism

(OCI-R) to see if there were any decreases from pre to post assessment. An additional secondary endpoint will be group differences on the behavioral tasks.

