### 5.0 Study Intervention

- 1.1 Description: Exposure-Based Perfectionism Treatment (EPT) involves repeated engagement in computerized tasks that instruct participants to purposefully make mistakes. There are three main tasks:

Misspelling Task: Participants will be presented with a phrase or a short sentence and be asked to copy that in the text box below. They will also be instructed to spell at least three words wrong in the sentence and then review the text as a whole after making the spelling errors. After they finish, they will click the next button and be given feedback stating that they copied the phrase or sentence incorrectly. This sequence will be repeated using different phrases or sentences, lasting approximately ten minutes total.

Simple Math Task: Subjects are presented with a simple math problem (e.g.,  $5+5$ ) and told to select the answer from the choices below within a 20 second time limit. The response options only include incorrect answers. After selecting a response, a feedback screen will appear stating that their response was incorrect. This sequence will be repeated with different simple math problems (addition, subtraction, multiplication, and division) for a total of approximately 10 minutes.

Shape Ordering Task: Subjects will be presented with a series of eight shapes, each shape lasting 1 second on screen, and be instructed to recall the order in which they were presented after viewing. Participants will be given 20 seconds to decide the order in which they think the shapes are presented before being automatically advanced to the next trial. After each trial they will be given feedback stating that their response was incorrect.

Distress Ratings: Before subjects begin the tasks and after the tasks end, participants will be asked to rate their current and peak levels of distress and frustration. Additionally, participants will rate characteristics of their perfectionism (using questions from the FMPS-CM) before and after the tasks.

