## PROTOCOL TITLE: An Exposure-Based Treatment for Perfectionism

2. Intervention Qualtrics Link: This link will include questionnaires asking about their perfectionism, mood, and behaviors. A detailed list of questionnaires is provided below. After completing questionnaires, participants will be directed to watch a pre-recorded video with study personnel providing information about perfectionism and the rationale of the intervention. They will also be informed that they will be asked to click on a link to complete the first intervention session immediately following this video and complete the intervention at home 4 times: 3, 6, 9, and 12 days after the baseline visit. A Qualtrics link to the first treatment session will be provided on the page after the video.

Those in the intervention group will then complete the first treatment session using the provided link. This will include three tasks, each targeting specific symptoms of perfectionism. Detailed information about the tasks is provided above. At the end of the treatment session, they will be directed to watch a video reminding them that they will receive Qualtrics links 4 times over the next two weeks: 3, 6, 9, and 12 days after the treatment. They will be instructed to complete each treatment session within 24 hours of receiving the link.

The first session will last approximately 45 minutes for those assigned to the wait list and 1 hour and 15 minutes for those assigned to the intervention.

Two weeks later, subjects will receive a Qualtrics link for the post-test assessment, in which the following will occur:

- The participants will be asked to complete questionnaires about their perfectionism, mood, and behaviors.
- Subjects will be debriefed.

Questionnaires:

Frost Multidimensional Perfectionism Scale (FMPS)

MINI International Neuropsychiatric Interview (MINI)

Structured Clinical Interview for the DSM-IV (SCID) Cluster C

Personality Disorder Modules

Eating Attitudes Test (EAT-26)

Center for Epidemiological Studies Depression Scale (CES-DS)

Social Phobia Index (SPIN)

State-Trait Inventory for Cognitive and Somatic Anxiety (STICSA)

Obsessive-Compulsive Inventory- Revised (OCI-R)

Error Sensitivity Index (ESI)

6.3

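### Section 6.2 randomises before the six secondary baseline scales are collected, so participants who stop at that step become avoidable post-randomisation losses; the harm is modest and reordering one survey flow prevents it

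*Combined protocol and SAP*

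**What the plan says.** Section 6.2 sets the order of events. The FMPS comes first: "After consenting, the participant will be directed to complete the FMPS". A remote clinical interview follows, then 1:1 randomisation, and only then the survey links: "Based on that randomization, they will be sent one to two Qualtrics links".

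Each arm has its own link, and each link opens with the baseline battery. The intervention link is described this way: "This link will include questionnaires asking about their perfectionism, mood, and behaviors". The wait-list link is described in the same terms. The questionnaire list in 6.2 contains the CES-DS, STICSA, SPIN, EAT-26, OCI-R and ESI, and no earlier administration of these six is described. The FMPS is on the list as well.

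The arm is disclosed after the battery. On the wait list: "After completing questionnaires, participants will be informed that they have been assigned to the wait list control group". In the intervention arm: "After completing questionnaires, participants will be directed to watch a pre-recorded video".

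The analysis needs these scores. Section 2.2 compares anxiety and depression "after controlling for baseline scores". Section 4.1 examines the six secondary scales "to see if there were any decreases from pre to post assessment". Section 17.1 names multiple regression by intent-to-treat and gives no rule for a missing baseline or post-test. Section 14.2 asks people who withdraw for a post-test, and 25.1 raises the sample from 68 to 80 for attrition.

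**The concern.** The baseline battery is a remote, self-administered step, and it falls between randomisation and treatment. Someone who abandons it is already in the intent-to-treat population but has no baseline on any of the six secondary scales. Two cases differ:

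- **They later give a post-test.** Their primary FMPS-CM comparison is intact, because the screening FMPS exists. In the secondary regressions, ordinary software drops a record with a missing covariate, and no pre-to-post change can be formed.
- **They give no post-test.** They are a randomised loss in every comparison, and the missing baseline adds nothing to that.

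In both cases the loss falls after randomisation only because of where randomisation sits in the flow. At stake are some precision on the secondary scales, part of the attrition allowance, and a secondary analysis set smaller than the randomised set that intent-to-treat promises.

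**Working it through.** **The plan's own figures.** The 68 in section 25.1 cannot be reproduced, because alpha, power, effect size and pre-post correlation are not stated. Several input sets give 68 at alpha 0.05 and correlation 0.5. Examples are a within-between effect f = 0.175 at 80% power, f = 0.20 at 90% power, or a between effect f = 0.30 at 80% power. The step to 80 is consistent with 15% attrition: 68/(1 − 0.15) = 80, an allowance of 80 − 68 = 12 people. The endpoint behind the 68 is not stated.

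**Order of events in 6.2.** Consent → FMPS → interview → randomisation → arm-specific link with the six secondary baselines → disclosure of arm. The primary scale is therefore measured before randomisation. The secondary scales are measured after randomisation but before participants are told their arm.

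**Loss of precision on the secondary scales.** The documents give no stopping rate, so 2, 4 and 8 of 80 (2.5%, 5%, 10%) are assumed. The standard error scales as √(80/remaining). The last column is an upper limit, because it counts every stopper as giving no post-test.

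| Stop | Remain | Standard error ratio | Share of the 12 |
|---|---|---|---|
| 2 | 78 | √(80/78) = 1.013 | 2/12 = 17% |
| 4 | 76 | √(80/76) = 1.026 | 4/12 = 33% |
| 8 | 72 | √(80/72) = 1.054 | 8/12 = 67% |

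**The same loss in power terms.** Assume a two-sided 5% t-test and d = 0.69, which gives 80% power at 34 per arm. With 15% post-test loss, 80 × 0.85 = 68 remain. If a further 5% or 10% lack a secondary baseline, 68 × 0.95 = 64.6 or 68 × 0.90 = 61.2 remain, and power is about 78% or 76%.

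**Recruitment under the reordered flow.** To randomise 80 when 2.5%, 5% or 10% stop at baseline: 80/0.975 = 82.1 (83), 80/0.95 = 84.2 (85), 80/0.90 = 88.9 (89).

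**Missing post-tests (secondary).** Suppose 6 of 40 intervention participants are lost and keep a fraction f of the benefit, while wait-list dropouts resemble the rest of their arm. Relative to the intent-to-treat effect, the observed-case estimate is 40/(34 + 6f), and imputing the 6 from the wait-list distribution gives 34/(34 + 6f).

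| f | Observed cases | Wait-list imputation |
|---|---|---|
| 1 | 40/40 = 1.00 | 34/40 = 0.85 |
| 0.5 | 40/37 = 1.08 | 34/37 = 0.92 |
| 0 | 40/34 = 1.18 | 34/34 = 1.00 |

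A simulation assumed 40 per arm, 6 lost per arm, pre-post correlation 0.6 and effect 0.7 SD; simulation error was about 0.01. Imputing from arm and baseline alone gave the same ratios as observed cases (0.99, 1.09, 1.18). Adding one session measure in the intervention arm moved the f = 0 ratio from 1.18 to 1.16, 1.12 or 1.06, for an assumed correlation with post-test, given baseline, of 0.3, 0.6 or 0.8. That assumes all 6 lost have the measure and that it reflects their smaller benefit.

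**How many session variables are usable.** Section 5.0 collects current and peak ratings of distress and frustration before and after the tasks, and adds that "participants will rate characteristics of their perfectionism (using questions from the FMPS-CM) before and after the tasks". That is 2 × 2 × 2 = 8 ratings per session. If they are taken at all five sessions, there are 40 ratings plus the FMPS-CM items, against 34 observed intervention post-tests. An ordinary imputation regression cannot carry them all.

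**The case against.** The strongest reply is that the harm is small and partly a matter of bookkeeping. A stopper who gives no post-test is lost whatever the order. One who does give a post-test stays in the primary comparison. Reordering retains nobody; it changes who is counted among the 80, and randomising a few more people under the present order would restore numbers in much the same way. All of this stands. What remains in favour of reordering is that every randomised person then has a full baseline, at almost no cost.

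Three stronger readings are tempting, and the documents do not support them:

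- **That answers are coloured by knowledge of the arm.** The questionnaires do follow randomisation, and the protocol labels the links by arm. But 6.2 places the wait-list notice and the rationale video after the questionnaires, and nowhere says that participants see the label. Loss at this step need not differ by arm.
- **That the plan excludes these participants.** No complete-case rule is written. Exclusion is a software default, and handling the missing covariate would keep anyone with a post-test.
- **That the primary comparison is biased.** The FMPS precedes randomisation. Regression on observed post-tests is biased only if loss is informative beyond arm and baseline, and the documents give no means of judging that.

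Sections 24.1 and 25.1 still place baseline in the laboratory, in conflict with the online flow in 6.2. That does not alter the order of randomisation and questionnaires.

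**Conclusion.** The point holds in limited form. Section 6.2 puts randomisation ahead of the only described baseline for six secondary scales, while 2.2 and 4.1 rely on that baseline. The consequence is avoidable loss of randomised participants and a modest loss of precision: standard errors about 1% to 5% wider on the secondary scales. This rests on an assumed 2 to 8 stoppers among 80 and on complete-case fitting, which the plan does not state. The primary FMPS-CM baseline is safe, although the FMPS appears both at screening and in the later battery and the plan does not say which score is the covariate.

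The silence on missing post-tests is mainly missing detail. It is worth closing so that the method is not chosen after the data are seen, but it does not show that the planned regression is wrong. The change is worth making because it is cheap, not because the trial is compromised without it.

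**What to change.** **Section 6.2.** Send one common baseline link to every eligible participant, randomise when it is completed, then branch to the wait-list notice or the intervention video. Name one pre-randomisation FMPS-CM score as the primary covariate. After reordering, both the screening score and the battery score qualify, so the choice only has to be stated in advance.

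**Section 17.1 (optional).** Suggested text: *All randomised participants are analysed by assigned arm. A participant with a post-test but a missing baseline is kept by imputing the baseline covariate. One sensitivity analysis imputes missing intervention post-tests from the wait-list distribution.* If session data are used in any imputation, name one or two summaries in advance, such as the last available FMPS-CM item score, and describe the result as reducing bias, not removing it.

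**Cost.** One survey flow is rearranged and a short paragraph added, with no new measures. People who stop at baseline no longer count towards the 80, so about 83 to 89 eligible people must start it if 2.5% to 10% stop (assumed). The sensitivity estimate will be less favourable, about 34/40 = 0.85 of the observed-case effect if 6 of 40 intervention post-tests are missing. Session summaries help only for participants who completed at least one session.

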### **4.0 Study Endpoints\***

**4.1** The primary endpoint will be scores from the Frost Multi-Dimensional Perfectionism Scale (FMPS)- Concern Over Mistakes Subscale. We will evaluate pre vs post differences. The secondary endpoint will include scores from the Center for Epidemiological Studies Depression Scale (CES-DS), the State-Trait Inventory for Cognitive and Somatic Anxiety (STICSA), the Social Phobia Inventory (SPIN), Eating Attitudes Test (EAT-26), Error Sensitivity Index (ESI), and the Obsessive-Compulsive Inventory- Revised

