## PROTOCOL TITLE: An Exposure-Based Treatment for Perfectionism

- To lessen the risks, participants will be explained what the treatment will look like and what the rationale behind it is before engaging in the intervention.
- All data collection materials can be found in the appendix of the IRB submission.

6.4 Data collected during the study will be obtained via self-report from subjects. Data will include demographics, information from a clinical interview, and self-report questionnaire responses.

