## 10.0 Subject Population\*

- 10.1 Students (ages 18-65) from the psychology subject pool will be recruited for the study. Additionally, participants from the community will be recruited for the study.
- 10.2 The subject population will consist of individuals with high levels of perfectionism (based on scores on the Frost Multidimensional Perfectionism Scale). Subjects must be between the ages of 18 and 65 and score at least a 29 on the FMPS. The FMPS cutoff score of 29 was chosen based on Shafran et al., 2017. Exclusion criteria include currently being in psychotherapy, had any changes to psychotropic medications in the past 4 weeks, current or past psychotic disorder or bipolar disorder, or current moderate or severe substance use disorder.

10.3 We will exclude the following populations:

- Adults unable to consent
- Individuals who are not yet adults (infants, children, teenagers)
- Pregnant women
- Prisoners

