### Intervention risks:

The perfectionism treatment is exposure-based, which means that it is expected to involve some discomfort for the subject. The treatment may lead to distress for subjects. They are told that they may feel psychologically uncomfortable, but that it is expected during this treatment. Participants will be able to stop treatment at any time. The benefits of exposure-based treatments have shown that though anxiety-provoking, the distress is temporary and there is often symptom-relief both in the short and long-term.

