### General Protection Against Risks:

At their request, participants will be referred to clinicians with whom they may speak about their discomfort or distress.

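### Only the wait-list arm is asked not to seek other treatment, and outside treatment is not a listed data item, so a difference in uptake between arms could enter the effect estimate unchecked.

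*Combined protocol and SAP*

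**What the plan says.** Section 6.2 describes the two arms in separate items. Under the Wait List Qualtrics Link, after being told their assignment, participants receive a request: "they will be asked to refrain from seeking treatment for perfectionism for the duration of the study". Under the Intervention Qualtrics Link the instructions concern the rationale video, the first session, the four later sessions and their timing, for example "They will be instructed to complete each treatment session within 24 hours of receiving the link". Nothing there concerns outside treatment, and no other section supplied puts such a request to that arm.

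At entry, Section 10.2 applies one rule to everyone: "Exclusion criteria include currently being in psychotherapy, had any changes to psychotropic medications in the past 4 weeks".

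At post-test, Section 6.2 says "The participants will be asked to complete questionnaires about their perfectionism, mood, and behaviors", followed by debriefing. The named instruments cover symptoms and diagnoses. Section 6.4 adds: "Data will include demographics, information from a clinical interview, and self-report questionnaire responses". Sections 4.1, 7.2 and 17.3 likewise do not name psychotherapy, self-help or medication change during the study.

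The primary endpoint is self-reported: "The primary endpoint will be scores from the Frost Multi-Dimensional Perfectionism Scale (FMPS)- Concern Over Mistakes Subscale". Section 17.1 specifies intent-to-treat multiple regression for the effect of condition and gives no rule for treatment started after randomisation.

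**The concern.** The entry criteria show that the sponsor regards concurrent treatment as a threat to interpretation. After randomisation that threat is handled differently by arm: one arm is asked to hold back and the other is asked nothing. If the request works as intended, it lowers uptake on the wait-list only. The comparison then drifts from the exposure tasks versus no treatment towards the exposure tasks plus whatever else participants take up, versus a group asked to take up nothing.

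Intent-to-treat analysis does not remove this. A comparison that includes outside help as it occurs is legitimate when both arms are equally free to seek it. Here part of any difference in uptake would come from the instruction, not from the intervention.

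The second part of the problem is that the listed data could neither show that uptake was negligible nor show which arm it favoured.

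**Working it through.** **Reading the arms side by side**

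| Item | Wait-list | Intervention |
|---|---|---|
| Entry restriction on psychotherapy and medication change (10.2) | Yes | Yes |
| Request not to seek treatment during the study (6.2) | Yes | None stated |
| Outside treatment as a listed data item (4.1, 6.2, 6.4, 7.2, 17.3) | None | None |
| Analysis rule for outside treatment (17.1) | None | None |

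The second row is the only one that differs by arm. The third and fourth mean that its consequence cannot be seen in the planned data.

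**Size**

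The plan gives no figure on this point to reproduce. The only document inputs are 40 per arm (12.1 and 25.1) and two weeks of participation (9.1). The rest is assumed: a baseline to post-test correlation of 0.6, two-sided alpha of 0.05, a benefit g of outside help in SD units, and uptake u_I and u_W in the intervention and wait-list arms.

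The standard error of the baseline-adjusted difference, in SD units, is

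SE = sqrt(2/40 × (1 − 0.6²)) = sqrt(0.05 × 0.64) = 0.179.

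Only the difference in uptake matters:

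bias = (u_I − u_W) × g.

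If the intervention itself does nothing, the chance of a significant result is P(|Z + bias/SE| > 1.96). With u_W = 0:

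| u_I | g (SD) | Bias (SD) | Bias/SE | Type I error |
|---|---|---|---|---|
| 5% | 0.25 | 0.0125 | 0.070 | 5.1% |
| 5% | 0.5 | 0.025 | 0.140 | 5.2% |
| 10% | 0.5 | 0.05 | 0.280 | 5.9% |
| 20% | 0.5 | 0.10 | 0.559 | 8.6% |

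For the last row, the upper tail beyond 1.96 − 0.559 is 0.0806 and the lower tail is 0.0059, which sum to 0.0865 (0.08650 before rounding, just under the halfway point).

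**Robustness**

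With a correlation of 0.5 and a noncentral t distribution, the last two rows become 5.8% and 8.0% at 40 per arm, and 5.6% and 7.6% at the 34 per arm that Section 25.1 gives before the attrition allowance.

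**Direction**

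With u_I = 20%, u_W = 10% and g = 0.5, the bias falls to (0.20 − 0.10) × 0.5 = 0.05 SD. Equal uptake gives zero. Higher uptake on the wait-list reverses the sign.

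**The case against.** The strongest reply is that the effect is trivial. Participation lasts two weeks, and people already in psychotherapy or with a recent medication change are excluded. The 8.6% figure needs one intervention participant in five to find, start and gain 0.5 SD from new help within 14 days, with nobody on the wait-list doing so. No figure in the documents supports that. This objection stands as to size. It does not explain why the request goes to one arm only.

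Four stronger readings are tempting, and the documents do not support them.

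- *All outside help in the intervention arm is credited to the intervention.* Only the difference between arms enters the estimate. The wait-list instruction is a request that participants may ignore, so the direction is plausible but not established.
- *The protocol prompts the intervention arm to seek help.* Section 15.1 expects distress from the tasks ("The perfectionism treatment is exposure-based, which means that it is expected to involve some discomfort for the subject"), but its referral provision is open to every participant and acts only on request: "At their request, participants will be referred to clinicians with whom they may speak about their discomfort or distress". The same section, under self-report measures, offers referral to clinical services to those seeking treatment after the study.
- *Outside treatment is not recorded.* Section 6.3 places the data collection materials in an IRB appendix that is not among the documents supplied, and the consent pages are not available either. Either could contain a question or a request to both arms. The questionnaire list is also not exhaustive: demographics are collected but not on it. What can be said is that the protocol does not list it.
- *Every rejection caused by uptake is a false positive.* Under an intent-to-treat reading, help-seeking that the intervention itself sets off is part of the effect of assignment. Only the part due to the unequal instruction is clearly an artefact of the design, so the type I error figures are an upper reading of the problem.

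**Conclusion.** The point holds in a limited form. As written, the protocol asks one arm and not the other to forgo outside treatment, and it lists no data from which the consequence could be judged. This is an asymmetric rule stated in the text, not merely missing detail.

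The bias would plausibly favour the intervention. Under the assumptions shown it is 0.0125 to 0.10 SD, with type I error between about 5.1% and 8.6%. That range rests on assumed uptake, benefit and correlation and on no wait-list uptake. Over two weeks the lower end is the more credible. The point is minor and does not by itself threaten the trial's conclusion. It merits a change because the remedy costs almost nothing.

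**What to change.** 1. Reconcile the two arm descriptions in Section 6.2 so that both arms receive the same wording on outside treatment. The choice of wording is the sponsor's. The referral and safety provisions in Section 15.1 stay as they are.
2. Add the same one or two questions to the post-test survey in both arms, covering psychotherapy, self-help programmes and medication change since baseline. If the IRB appendix already has them, say so in Sections 6.2 and 6.4.
3. Report the answers descriptively by arm.
4. Keep the intent-to-treat regression as the primary analysis and do not adjust it for treatment use. Uptake arises after randomisation and may be affected by assignment, so conditioning on it could introduce bias.

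The cost is one line in the participant instructions and one or two survey items.
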